In Specific Aim 1, we aim to demonstrate differences in propofol sensitivity across 2 patient cohorts based on the presence of absence of basal ganglia pathology (Parkinson disease [PD] and essential tremor, respectively). By characterizing and demonstrating differences in group level pharmacokinetic/pharmacodynamics of propofol (primary endpoints), we will provide evidence suggesting basal ganglia pathology is associated with differential response to propofol suggesting the basal ganglia are an important part of brain circuitry regulating consciousness. This aim will be completed entirely at UCLA.

In Specific Aim 2, we aim to characterize the temporal evolution of brain signals (recorded from the cortex and the basal ganglia) with propofol induced loss and recovery of consciousness to identify network level changes correlating with consciousness. All subjects will have PD and will be assigned to the same intervention of propofol administration and withdrawal, while we invasively record brain signals from key nodes in the hypothesized brain networks regulating consciousness. The primary endpoint/outcome will be neurophysiologic data.

In Specific Aim 3A, we aim to demonstrate the role of the basal ganglia in regulating consciousness by focally modulating the network with deep brain stimulation (DBS). Patient with PD and previously implanted DBS will be randomly assigned to undergo anesthetic induction either with or without DBS. Primary endpoint will be the characterization of the pharmacokinetics/pharmacodynamics with and without stimulation with PD. We expect to see shifts in the kinetics and dynamics associated with DBS, suggesting focal modulation of the circuit alters consciousness regulating circuitry of the brain.

In Specific Aim 3B, we will conduct a final clinical trial in which we will, as in Aim 3, record from the brain of patients undergoing DBS implantation, now with or without DBS on during both induction and emergence from propofol anesthesia. The primary outcome will be neurophysiological signals and observing perturbations of the evolution of the brain signals with vs without DBS.

2. Background.

- Describe past experimental and/or clinical findings leading to the formulation of your study.
- For research involving investigational drugs, describe the previously conducted animal and human studies.
- For research that involves FDA approved drugs or devices, describe the FDA approved uses of this drug/device in relation to your protocol.

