Specific Aim 1: The overall goal for this aim is to assess the population level pharmacokinetic-pharmacodynamic (PK-PD) model for propofol sedation in *PD patients (who have BG pathology) in contrast to a control group (essential tremor, ET, who do not have BG pathology)*. The PK-PD model will be used to predict the time course of plasma and effect site concentration of propofol and establish differential anesthetic sensitivity profiles. This assessment will be done during battery placement surgeries for individuals already implanted with DBS electrodes.

Specific Aim 2: These experiments will be performed during the initial DBS implantation surgery. The overall goal for this aim is to assess neural correlates, with specific attention to network parameters/states, during LOC/LOR and ROC/ROR using direct, high-resolution invasive recordings from the basal ganglia (GPi/GPe) and frontoparietal cortices in humans. *There is only one study group in this aim – PD patients (no stimulation of GPi/GPe).*

Specific Aim 3a: These experiments will be performed during the DBS generator exchange surgeries, as in Aim 1. All study participants will have PD in this set of experiments and results will be compared across *experimental cohorts (GPi vs GPe stim)* as well as to PD patients anesthetized with propofol off stimulation (from Aim 1). During data analysis, the rater will be blinded to stimulation assignment.

Specific Aim 3b: These experiments will be performed during the initial DBS implantation surgery. Recordings and behavioral assessments will be made during both induction and emergence of anesthesia with *either GPi or GPe stimulation*, comparing results with those acquired in Aim 2 (no stimulation). As in Aim 3a, the rater will be blinded to stimulation assignment.

4. Research Plan / Description of the Research Methods:

4.a. Provide a comprehensive narrative describing the research methods.

- 1) Provide the **order in which tests/procedures will be performed**,
- 2) Provide the **setting** for these events and a description of the **methods used to protect privacy** during the study.
- 3) Provide the **plan for data analysis** (include as applicable the **sample size calculation**)

Please respond to all components of this item, or clearly indicate which components are not applicable.

Some information in responses below is taken from grant protocol section 3 "Approach". See figures referenced and citations in grant protocol.

RESEARCH METHODS

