Target-Controlled Infusion (TCI) Anesthesia protocol. We will use a syringe pump controlled by STANPUMP implementing the Eleveld Pharmacokinetics-Pharmacodynamics (PK-PD) model for propofol as a TCI system to achieve plasma target propofol concentrations.⁵⁷ Two intravenous cannulae will be used in each patient, one for propofol infusion and one for blood draws. Supplemental oxygen will be delivered as needed by nasal canula. Propofol serum concentrations will be confirmed via blood sampling to confirm the TCI performance. Blood samples will be stored on ice until they can be centrifuged, and the plasma fraction isolated by centrifuge and stored at -20 deg C until analyzed. Propofol concentration will be determined by a high performance liquid chromatographic method (HPLC).⁵⁸ The attending anesthesiologist will be able to override the pump at any point should there be evidence of airway obstruction, hemodynamic compromise, or other clinical issue, though the long track record of safety of TCI systems outside of the United States suggests this should not be a major issue, and TCI models appear safe to use in PD patients.⁴⁷ Per prior published work⁴⁸, target effect-site concentration of propofol will be started at 1.4 µg/mL (below expected level required for LOC/LOR) and will be increased by 0.3 µg/mL with reassessment until endpoints are achieved. ROC/ROR will be assessed with gradual reduction in propofol dose as with assessment of relevant endpoints. Due to clinical and invasive neurophysiological requirements, in all cases, ROC/ROR will be evaluated after LOC/LOR.

Specific Aims 1 & 3a:

Data collection for these aims will occur during IPG placement / replacement surgery for individuals with DBS. Specific Aim 1 will occur solely at UCLA following these guidelines. Specific Aim 3a will be collected at both UCLA and UTSW following the same protocol.

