Behavioral data analysis and constructing propofol dose response curve. Behavioral data will be collected from both PD and ET patients undergoing generator replacement surgery. Propofol will be administered using a recently published, unified PK-PD for propofol developed to predict the BIS (bispectral index) response to propofol for a broad, diverse population by Eleveld and colleagues, which includes age adjustment, allometric scaling, and parameters for arterial and venous sampling.⁵⁷ (Although not a focus of our work and its value questionable given our underlying hypothesis of altered mesocircuit function in PD, we will record BIS in all patients as an additional data point.) From a range of studies, we expect that in a healthy population loss of responsiveness in 50% of healthy patients will occur with an age-adjusted effect site concentration (Ce₅₀) between 2.71–3.44 µg/ml.⁷⁴ The only published pharmacodynamic studies in PD patients reported a Ce₅₀ of 2.05 and 2.28 µg/ml.^{47, 48} We therefore expect that the dose-response curve for PD patients will be shifted to the left compared to ET patients, who lack basal ganglia pathology. To test this hypothesis, propofol infusion will be initiated with an effect-site concentration (Ce) target of 1.4 µg/ml for 5 min, incremented by 0.3 µg/ml steps every 5 min until loss of behavioral responses (as defined in 3.1.4). One additional incremental step will be performed after loss of responses. Venous serum samples will be drawn at the end of each 5 min step before the next increment. After conclusion of the procedure, target Ce would decrement by 0.3 µg/ml every 5 min until recovery of behavioral responses. Serum sampling will be used to confirm that the Eleveld unified TCI model is functioning as predicted.

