PK-PD Model Fitting. The pharmacodynamic responses for both behavioral endpoints will be modeled with a sigmoidal E_{max} function: $Fraction_{responsive} = 1 - C_e^{\gamma} / (C_{e50}^{\gamma} + C_e^{\gamma})$; Where Ce is the effect site concentration, Ce₅₀ is the effect site concentration at which half of the population is no longer responsive, and γ is the Hill coefficient governing the slope of the sigmoid. Fitting will be done using NONMEM (ICON Development Solutions) and parameter estimation. Comparison of Ce₅₀ values between PD and ET populations will be made using 95% confidence limits on the resulting parameter fits. Additional exploratory analyses of the model will attempt to account for heterogeneity in the PD population by constructing candidate models that nest the PD effect by both UPDRS scores and covariates of cognitive function (MoCA), utilizing a drop of corrected Akaike Information Criterion (AIC) by 20 points as a threshold for a significant improvement from adding a parameter to the model.

Specific Aim 2:

We will temporally correlate the evolution of behavioral measures of LOC/LOR (including loss of spontaneous movement and loss of movement to command, with digital synchronization with neurophysiological recordings through digital event recording) with I changes in GPi vs GPe pallidocortical circuits. Techniques outlined in LFP analyses above will be implemented to complete assessment.

Specific Aim 3a:

Statistical analysis pipeline outlined in Aim 1 will be replicated in Aim 3a.

Specific Aim 3b:

Recordings and behavioral assessments will be compared to results acquired in Aim 2. Techniques outlined in LFP analyses above will be implemented to complete assessment.

SAMPLE SIZE

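### Pharmacokinetics are part of the primary endpoint in Aims 1 and 3A, but no pharmacokinetic contrast is specified and the assays are not said to inform Ce, so a concentration error that differs between groups would pass into Ce50

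*Combined protocol and SAP*

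**What the plan says.** All references are to the combined protocol and SAP.

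- **Endpoint.** Section 1, Specific Aim 1, rests its inference about the basal ganglia on "differences in group level pharmacokinetic/pharmacodynamics of propofol (primary endpoints". For Aim 3A it says: "Primary endpoint will be the characterization of the pharmacokinetics/pharmacodynamics with and without stimulation with PD". It adds: "We expect to see shifts in the kinetics and dynamics associated with DBS".
- **Source of concentrations.** Section 3, Specific Aim 1: "The PK-PD model will be used to predict the time course of plasma and effect site concentration of propofol".
- **Samples.** Section 4.a, Data Analysis, Specific Aim 1: "Venous serum samples will be drawn at the end of each 5 min step before the next increment". The assay is HPLC.
- **Use of the assays.** It is stated twice, both times as confirmation. The target-controlled infusion (TCI) paragraph of section 4.a says "Propofol serum concentrations will be confirmed via blood sampling to confirm the TCI performance", and the Aim 1 analysis says "Serum sampling will be used to confirm that the Eleveld unified TCI model is functioning as predicted".
- **Model.** Under PK-PD Model Fitting: "The pharmacodynamic responses for both behavioral endpoints will be modeled with a sigmoidal" Emax function. Its parameters are Ce50 and a Hill coefficient, and Ce50 is compared between Parkinson disease and essential tremor by 95% confidence limits. No clearance, volume or effect-site rate constant is named.
- **Aim 3a** repeats the Aim 1 analysis.
- **Sample size.** The simulations for Aims 1 and 3a let the two populations differ in Ce50 alone.

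**The concern.** Two consequences follow from the text as written.

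First, half of a named primary endpoint has no estimator. No pharmacokinetic parameter, group contrast or measured/predicted summary is specified, although Aim 3A expects the kinetics to shift. This holds whatever the size of any pharmacokinetic difference.

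Second, Ce50 is expressed in units of whatever Ce enters the fit. If that is the prediction of a general-population model, and true concentrations depart from prediction differently in the two groups, the departure appears as a difference in Ce50. The protocol would read that as a difference in the sensitivity of the brain, which is the central inference of Aim 1. The error can also run the other way and hide a real difference.

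**Working it through.** **Inputs from the documents** (Sample Size, Aim 1): planned Ce50 difference 20%; between-patient variability 20%; an additive measurement error of unstated size; about 24 per arm for 80% power. The 95% limits imply a two-sided 5% level.

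**Assumed inputs:** the group difference b in measured/predicted concentration, and that a proportional plasma error carries through to the effect site. The documents give neither.

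**1. The plan's own figure.** The 24 per arm cannot be reproduced strictly, because the additive error, the Hill coefficient and the success criterion are not given.
- From 20% and 20% alone, n = 2 × (1.960 + 0.842)² × 0.20² / 0.20² = 15.7, so 16 per arm. Power at 24 is 93%.
- An added relative error of 0.145 makes the SD √(0.20² + 0.145²) = 0.247, which gives 24.
- A Monte Carlo run (500 trials per setting; essential tremor Ce50 assumed 2.85 µg/mL; additive SD assumed 0.2 µg/mL) gives 79% power at 24 per arm if success means non-overlapping 95% intervals.

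So 24 is attainable under plausible assumptions. SDs of 0.20 and 0.247 are used below as the range.

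**2. The bias.** Let true concentration in Parkinson patients be (1+b) times predicted, relative to essential tremor, with equal true Ce50. Response is then lost at a predicted Ce lower by the factor 1/(1+b), so the apparent Ce50 ratio is 1/(1+b). A factor common to both groups cancels.

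**3. Chance of a significant Ce50 difference with none present, 24 per arm.** With d = 1 − 1/(1+b) and se = SD × √(2/24), the probability is Φ(d/se − 1.96) + Φ(−d/se − 1.96).

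Example, b = 20%: d = 1 − 1/1.20 = 0.167. For SD 0.247, se = 0.0713, d/se = 2.34 and Φ(0.38) = 0.65. For SD 0.20, se = 0.0577, d/se = 2.89 and Φ(0.93) = 0.82.

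| Assumed b | Apparent Ce50 ratio | P(significant), SD 0.247 | P(significant), SD 0.20 |
|---|---|---|---|
| 0 | 1.00 | 5% | 5% |
| 5% | 0.95 | 10% | 13% |
| 10% | 0.91 | 25% | 35% |
| 15% | 0.87 | 45% | 62% |
| 20% | 0.83 | 65% | 82% |
| 25% | 0.80 | 80% | 93% |

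**4. Monte Carlo check.** With equal Ce50, b = 20% and additive SD of 0 or 0.3 µg/mL, the estimated ratio is 0.83. A false difference appears in 76–87% of trials by a Wald test and 48–64% by non-overlap of intervals. With b = 0 the rates are 5–7% and about 1%.

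**5. Masking.** With a true Ce50 ratio of 0.80 and Parkinson concentrations 10% below prediction, the apparent ratio is 0.80/0.90 = 0.89 and power is 34–49%. At 20% below it is 0.80/0.80 = 1.00, and the real difference is fully hidden.

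**6. Sampling.** Table 4.d lists 3–5 blood draws, while the Aim 1 analysis describes one per step. With steps of 0.3 from 1.4 µg/mL, the fifth is at 1.4 + 4 × 0.3 = 2.6 µg/mL. That is below the 2.71–3.44 µg/mL range the protocol expects for Ce50 in healthy patients, which is reached at steps 6 to 8.

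**The case against.** **A pharmacokinetic fit may be intended.** The paragraph is headed PK-PD Model Fitting, the software is NONMEM, section 3 speaks of a population PK-PD model, and the protocol defers to a grant document that is not part of this record. The model paragraph never says outright whether Ce is the target, the prediction or an updated value. This stands. A reader might infer that the assays will never enter any estimation; the documents show only that no such use is stated.

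**The planned check could reveal the problem.** Measured and predicted concentrations will exist for both groups. This also stands, so it would be wrong to say that the trial's data cannot separate kinetics from sensitivity. What is missing is a group-wise measure, a threshold and a stated consequence for the Ce50 comparison.

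**The size is hypothetical.** No document figure supports any b. The protocol says that the published model already includes age adjustment, allometric scaling and venous-sampling parameters, which should reduce group differences that arise from age or body size. In Aim 3a all patients have Parkinson disease, so an error tied to the disease itself cancels there. These limits stand; the table shows a range, not a prediction.

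**A full model is too much for these data.** Disease effects on clearance and several volumes would be weakly identified from a few venous samples during a short infusion. This stands and limits the fix.

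**Conclusion.** The concern holds as a gap in the specified analysis of Aims 1 and 3a. Pharmacokinetics belong to the primary endpoint, the stated pipeline estimates no pharmacokinetic contrast, and no passage says that the assays inform Ce. Followed as written, with Ce predicted as section 3 indicates, a between-group factor of 1+b in measured/predicted concentration moves the Ce50 ratio to 1/(1+b). A difference of 25% would reproduce the whole planning effect.

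This rests on model-predicted Ce entering the fit, on the plasma error carrying through to the effect site, and on assumed values of b.

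A reader might go further and infer that a left-shifted Parkinson curve would be a pharmacokinetic artefact, or that 24 per arm is wrong. The documents support neither. They give no evidence of a group difference in concentration error, and 24 is compatible with the stated inputs once a plausible measurement error is added.

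**What to change.** For Aims 1 and 3a:

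1. State which Ce enters the Emax fit.
2. Report the measured/predicted concentration ratio by group (diagnosis in Aim 1, stimulation condition in Aim 3a) with a 95% confidence interval, using the published model's venous prediction. This is the pharmacokinetic comparison.
3. Estimate Ce50 with Ce updated from each patient's measured concentrations, taking the published model as prior and a parsimonious group term on the pharmacokinetics. Report it beside the Ce50 from model-predicted Ce.
4. Attribute a Ce50 difference to brain sensitivity only if it persists after this correction. Otherwise narrow the claim, or remove pharmacokinetics from the primary endpoint.

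Two sets of statements must also be reconciled: the plasma-target and effect-site-target wording in the TCI paragraph, and the 3–5 draws in table 4.d against one draw per step in the Aim 1 analysis.

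**Cost.** Samples and assays are already planned, so most of this is analysis work. The update needs a timed dosing record that covers pump overrides and any propofol given clinically beforehand; no passage plans to capture the latter. The Ce50 interval will widen. Venous samples do not identify the effect-site delay, so that part of Ce stays model-assumed and the correction removes plasma error only.

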For all specific aims:

Prior to conducting any research related tests / procedures, the patient will be consented. The consent process will be facilitated by the IRB approved research coordinator and will occur in a private room in the pre-operative area prior to surgery. Once in the operating suite, the patient will be put under anesthesia for clinical purposes for surgery. Privacy will be maintained by limiting the individuals in the operating room to only necessary IRB approved research personnel. In addition, all data collected during the study will be immediately de-identified and stored on an encrypted, password protected server.

Behavioral Assessments. For each experiment, three behavioral responses will be evaluated: (1) loss/recovery of spontaneous movement (i.e., loss and recovery of responsiveness (LOR/ROR)) (2) loss/recovery of movement in response to stimuli (separately to clicks [non-salient] and verbal stimuli [salient], as per prior work by Purdon and colleagues⁴), and (3) loss/recovery of movement to command (verbal command with patient name with instruction to show different numbers of fingers, as proxy of loss/recovery of consciousness (LOC/ROC)). Stimuli will be presented in an interleaved fashion every 4 seconds binaurally via headphones (15 presentations of each stimuli at each dose, total 5 min per dose, or until failure to respond 3 times in a row to a certain stimulus). We use these separate measures because of the literature and our hypothesis that circuits mediating responsiveness and consciousness are separable. Namely, numerous studies highlight that consciousness (defined as ability to interact with the environment, most often measured by the isolated forearm test) can be maintained even with loss of responsiveness.^{39, 56}

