Surgeries are performed under monitored anesthesia care, using propofol anesthetic. Once patients are positioned, propofol is administered per a target-controlled infusion (TCI) anesthesia protocol detailed above. Participants will also complete the Behavioral Assessments outlined above. Assessment will be completed at the end of every propofol infusion (every 5 minutes). Blood draw will also occur at this time. If data is being collected for **Specific Aim 1**, no DBS stimulation will occur. If data is being collected for **Specific Aim 3a**, the patient will receive either GPi or GPe stimulation during study tasks. Once stable anesthesia is established, local anesthetic is infused and the generator is replaced, prior to closing the skin. Behavioral assessments will be made during induction and / or emergence.

Specific Aims 2 & 3b:

Data collection for these aims will occur during DBS implantation surgery. Data will be collected at UCLA and UTSW following the same protocol.

Surgical procedure Intraoperative Recordings (Specific Aim 2, 3). For DBS implantation for PD, the DBS lead is targeted to ventral posterolateral GPi using image-guided targeting (2-4 mm anterior, ¹⁹⁻²⁴ mm lateral, and 4-6 mm inferior to the mid-commissural point [MCP], Figure 4). All trajectories are confirmed with intraoperative microelectrode recordings, based on firing activity and kinesthetic tests⁵² in addition to intraoperative awake macrostimulation testing, clinically assessed by [name]. LFP will be recorded from deep brain targets from the DBS lead's four or eight contacts (dependent on clinical selection of DBS

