The patient will emerge from anesthesia for clinical placement of the left DBS electrode and neurological testing done by [name] and the neurologist. Once clinical testing is complete, the ECoG strip will be placed on the right side for research purposes. Then, [name] will continue with the clinical procedure and place the right DBS electrode and conduct neurological testing to confirm placement. The researchers will connect ECoG and DBS leads to the Neuro-Omega system to record brain signals throughout research related tasks. Once all clinical testing has been completed, the research team will simultaneously record cortical ECoG and pallidal LFP from GPI/GPe during both induction and emergence with target-controlled infusion of propofol detailed above. During induction and emergence, the participant will also complete the behavioral task detailed above. If data is being collected for **Specific Aim 2**, ECoG /LFP recordings and behavioral assessments will take place with no stimulation. If data is being collected for **Specific Aim 3b**, recordings and behavioral assessments will be made during both induction and emergence of anesthesia with either GPI or GPe stimulation. When the research portion is complete, the ECoG strips will be removed and the surgery will finish per clinical standard of care.

DATA ANALYSIS

LFP Analyses:

Signal analysis is performed in MATLAB (The Mathworks Inc., Natick, MA). Data is parsed into various behavioral and stimulation state epochs, excluding any sections containing electrical or movement artifact using methods previously described.^{41, 50} Bipolar re-referencing of adjacent contacts is used in order to emphasize local and minimize global signals, which is critical for the proposed network coupling analyses across brain regions. 60 Hz line noise is rejected using a notch filter. 60 Hz line noise is rejected using a notch filter.

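### Aim 3b's with-versus-without-stimulation contrast uses the separately labelled Aim 2 cohort as its control, and no randomization or concealed allocation between the two is stated

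*Combined protocol and SAP*

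**What the plan says.** **Condition by aim.** Section 4.a, Specific Aims 2 & 3b, sets stimulation by the aim for which data are collected. For Aim 2, "ECoG /LFP recordings and behavioral assessments will take place with no stimulation". For Aim 3b, "recordings and behavioral assessments will be made during both induction and emergence of anesthesia with either GPI or GPe stimulation".

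**Comparator.** Section 3 names the unstimulated Aim 2 results as the reference for Aim 3b. The Aim 3b analysis paragraph agrees: "Recordings and behavioral assessments will be compared to results acquired in Aim 2".

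**Setting.** Both aims take Parkinson disease patients at initial DBS implantation. "Data will be collected at UCLA and UTSW following the same protocol".

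**Random assignment.** It is stated once, in section 1 for Aim 3A, whose patients "will be randomly assigned to undergo anesthetic induction either with or without DBS". Nothing similar is stated for choosing between Aims 2 and 3b, or between GPi and GPe within Aim 3b.

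**Consent.** It "will occur in a private room in the pre-operative area prior to surgery". No section says when a patient's aim is chosen or disclosed.

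**Protection and analysis.** Section 3 blinds the Aim 3b rater to stimulation assignment. The Statistical Analysis paragraph plans t-tests between conditions and states no adjustment for site, cohort or calendar time.

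**Text that does not fit.** Section 1 describes Aim 3B as "now with or without DBS on during both induction and emergence from propofol anesthesia", which can be read as an off condition inside Aim 3b. The section 4.c table for GPi/GPe stimulation lists Aim 2 among the exposed groups.

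**The concern.** Aim 3 is meant to support a causal statement: that focal modulation of the basal ganglia changes the circuitry regulating consciousness. For Aim 3b, that statement rests on a difference between two cohorts whose members are placed in one or the other by a process that the protocol does not describe.

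Anything that differs between the cohorts besides stimulation enters the contrast. Three sources can be seen in the documents:

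- which patients are put into which aim;
- the mix of UCLA and UTSW patients;
- the lead, which has four or eight contacts by clinical choice and is the source of the pallidal recordings.

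A fourth, drift in technique or case mix over time, applies only if the aims are enrolled one after the other. Any such difference would be reported as an effect of stimulation.

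**Working it through.** **1. Reproduce the plan's figure.** The Sample Size section gives 16 patients for Aim 3b (one-sample t-test, d = 0.75, power 0.8, α = 0.05), in the same words as for Aim 2. The noncentrality is 0.75 × √16 = 3.0 on 15 df. Two-sided exact power is 0.801 (0.771 at n = 15), so 16 reproduces. With 20% dropout, 16 / 0.8 = 20, as stated. This figure is for a within-patient change from rest to the anesthetized state. It is not for Aim 3b against Aim 2.

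**2. Effect of a cohort difference when stimulation does nothing.** Suppose that the compared measure differs between cohorts by b SD for reasons other than stimulation. The two-sample t statistic then has noncentrality b × √(n₁n₂/(n₁+n₂)) on n₁+n₂−2 df. The rejection probability at two-sided 5% is the false-positive rate. The values of b are assumptions, because the documents give none.

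| Comparison | Multiplier | b = 0.3 SD | b = 0.5 SD |
|---|---|---|---|
| 16 v 16 (GPi and GPe pooled v Aim 2) | √(256/32) = 2.828 | noncentrality 0.849, 13.0% | noncentrality 1.414, 27.8% |
| 8 v 16 (one target v Aim 2, even split assumed) | √(128/24) = 2.309 | noncentrality 0.693, 10.2% | noncentrality 1.155, 19.7% |
| 20 v 20 (no dropout) | √(400/40) = 3.162 | noncentrality 0.949, 15.2% | noncentrality 1.581, 33.8% |

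Smaller shifts do less harm: at 16 v 16, 0.1 SD gives 5.9%. Larger cohorts do not cure the problem, because a fixed bias is detected more often as n grows.

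**3. Drift, if the aims are sequential.** Linear drift was simulated over 32 consecutive patients, with the first 16 off and the last 16 on. Total drift of 0.5, 1.0 or 1.5 SD gave false-positive rates of 10.6%, 27.8% and 54.5%. With the same drift and concurrent random allocation, the rate stayed at about 5%.

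**4. Power of the contrast.** If d = 0.75 also applied to on versus off, the noncentrality at 16 v 16 would be 0.75 × 2.828 = 2.121 and power 0.54. At 8 v 16 power would be 0.38. Power of 80% needs 29 per arm.

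**5. Allocation ratio for a pooled design.** Equal three-way allocation of 40 gives 40/3 ≈ 13 off patients, or about 11 evaluable after 20% dropout. That is below the 16 that Aim 2 requires. A 2:1:1 ratio gives 20, 10 and 10, or 16, 8 and 8 evaluable.

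**The case against.** **A reader might infer more than the documents say.**

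- *That on or off is known before consent, and so is predictable for every patient.* The documents do not support this. They give the place and timing of consent, but not the point at which a patient's aim is fixed. On or off follows once the aim is known, and GPi or GPe may still be open.
- *That the off patients are enrolled first.* Section 1 presents the aims in sequence and describes Aim 3B as the last trial, but this may be only order of presentation. There are no dates, and no rule that Aim 2 closes before Aim 3b opens. Drift is a conditional risk.
- *That section 4.a settles who is stimulated.* Sections 1 and 4.c contain text that does not fit it.

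**The rater is blinded.** This limits assessment bias. It does not affect who enters each cohort, or when.

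**The compared quantity may be a within-patient change.** The sample size is built on such a change. If it is what is compared, stable additive offsets from site or lead type largely cancel. This stands, so b in the table must be read as a difference in the compared measure itself. A difference between cohorts in the change would not cancel.

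**The sizes are assumed.** This stands too. One route to 0.3 SD is a 1 SD difference between sites with the site mix moving from 50% to 80%: (0.80 − 0.50) × 1 = 0.30 SD. Both inputs are assumptions. If the 1 SD is measured within site, mixing sites also widens the outcome SD, and simulation gives about 11.7% in place of 13.0%.

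**Conclusion.** The concern holds in this form. As written, the Aim 3b primary contrast is a non-randomized comparison with a separate cohort. Nothing stated prevents or adjusts for selection or for imbalance in site or lead type, or for drift if enrolment is sequential. This follows from sections 3 and 4.a without any assumption about timing.

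Its size is not known from the documents. Under assumed shifts of 0.3 to 0.5 SD in the compared measure, the false-positive rate is 13% to 28% at 16 v 16. It is 10% to 20% for a single target at 8 v 16, where an even GPi/GPe split is also assumed. These figures show sensitivity and do not estimate the bias that will occur.

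The descriptions of who receives stimulation in sections 1 and 4.c conflict with sections 3 and 4.a and must be reconciled. An off condition inside Aim 3b would not settle the matter, because section 1 states no randomization for it.

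**What to change.** 1. Enrol the planned Aim 2 and Aim 3b patients (at least 20 + 20) as one concurrent implantation pool.
2. Allocate off:GPi:GPe in the ratio 2:1:1 from one central, concealed, computer-generated list, stratified by site with varying block sizes. About 20 off patients (16 evaluable) then remain for Aim 2.
3. Reveal the assignment only after consent and after clinical testing is complete.
4. Use the off patients for Aim 2. Analyse Aim 3b as the randomized comparison with a site term.
5. State this consistently in section 1, section 3, the Aims 2 & 3b timeline in section 4.a and the Aim 3b analysis paragraph. Reconcile the list of exposed groups in section 4.c.
6. State that the on-versus-off contrast is not powered by the planned numbers: about 0.54 at 16 v 16 if d = 0.75 applied.

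The cost is a protocol and consent amendment and one randomization list. Planned patient numbers and study procedures stay as they are under the 2:1:1 ratio. The main drawback is that Aim 2 finishes later, because its patients are enrolled alongside those of Aim 3b. The change removes systematic allocation bias but does not add power. It is hard to make once Aim 2 patients have been enrolled alone.
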